## C6. MBC Fidelity

In this proposal, fidelity to MBC is a three-level categorical variable defined by (a) client completion of the PHQ-9 (No=0, Yes=1), (b) clinician review of scores in the electronic health record (No=0, Yes=1), and (c) discussion of scores in session (No=0, Yes=1). The former two (PHQ-9 completion and clinician review of scores) will be automatically captured through the electronic health record. Clinicians will also check a box in the electronic health record progress note to indicate if they discussed scores in session, as this practice optimizes the effectiveness of MBC (Eisen, Dickey, & Sederer, 2000). Given the known limitations to clinician self-report, this latter fidelity criterion will also be assessed with client self-report via an automated telephone survey immediately after their session. In their first month of implementation, all clinicians (regardless of condition) will be asked to indicate factors they perceived to have limited MBC use. Through a drop-down menu embedded in the electronic health record progress note, clinicians will select contextual factors based on the literature (Dowrick et al., 2009; Garland, Kruse, & Aarons, 2003; Valenstein et al., 2009) and clinician-identified factors (from our pilot data); See Appendix for complete list of options (e.g. lack of time, client refused, clinician forgot).

## C7. The Evaluation Process

Figure 1 depicts the Framework for Dissemination, which outlines the diffusion and evaluation processes for this study ([name], Meredith, Shoenbaum, Sherbourne, & Wells, 2008). Contextual factors (Box 1) theorized to influence the stages of diffusion (Box 2) are identified and both individual and organizational outcomes are considered (Box 3). This framework is based upon the best available research and includes a 3-phase evaluation process (see bottom row) with a community partnership emphasis directly suited to guide this proposal. This model will allow us to evaluate the standardized implementation protocol and to identify contextual factors that may limit or facilitate its effectiveness. This model will also be used to guide the tailored approach to implementation ([name]; Letter of Support).

**Figure 1. Framework for Dissemination**

**C8. Complementary Testable Model.** Chambers, Glasgow, and Stange (2013) recently put forth the Dynamic Sustainability Framework to promote testing of falsifiable hypotheses that program drift from "fidelity" of evidence-based practices leads to a voltage drop in implementation outcomes as compared to effect sizes observed in efficacy trials. Chambers et al. (2013) contend that an alternative hypothesis is important to consider: intentional adaptations to EBP implementation that are informed by community

stakeholders and account for relevant multi-level contextual factors may optimize sustainment and intended outcomes. This proposal intends to test this model. Specifically, the standardized condition requires (via a guideline) that MBC be implemented weekly prior to each psychotherapy session according to its documented efficacy (e.g., Bickman et al., 2008; Whipple et al., 2003). Conversely, the tailored condition will allow the implementation team at each site to adapt this guideline, taking into account their specific context (e.g., monthly MBC implementation).

## **C9. Pilot Studies**

Two Centerstone sites participated in our pilot study to assess the feasibility of the implementation and evaluation process and to inform the implementation protocols for this proposal (*C10. Multifaceted Protocol*).

**Baseline Needs Assessment.** The mixed methods needs assessment included baseline in-person clinician ( $N=10$ , 1.5 hours) and client ( $N=6$ , 1 hour) focus groups and clinician ( $N=24$ ) self-report survey assessments to evaluate the contextual factors of diffusion (Box 1, Figure 1). This needs assessment procedure proved successful for data collection and resulted in 100% clinician participation. At baseline, the Attitudes towards Standardized Assessment scale (ASA, scale ratings 1-5; Jensen-Doss & Hawley, 2010) indicated that clinicians at both sites had generally neutral attitudes about MBC practicality ( $M=3.03$ ,  $SD=0.54$  and  $M=3.14$ ,  $SD=0.42$ , respectively; Cohen's  $d=0.23$ ), its benefit over clinical judgment ( $M=2.88$ ,  $SD=0.46$  and  $M=3.40$ ,  $SD=0.93$ , respectively; Cohen's  $d=0.71$ ), and its psychometric quality ( $M=3.37$ ,  $SD=0.56$  and  $M=3.89$ ,  $SD=0.53$ , respectively; Cohen's  $d=0.95$ ), with Site A demonstrating moderately lower scores across the subscales. Sites also differed on their intention to use MBC; Site B had more positive views of social influence to use MBC ( $t=2.48$ ,  $p=.042$ ) and MBC self-efficacy ( $t=3.49$ ,  $p=.010$ ).

Qualitative analyses of clinician focus groups (2 sites,  $N=10$ ) also revealed site differences in implementation barriers. Notably, significant site differences were observed in the ratio of negative to positive attitudes about MBC (Site A: 44 negative to 17 positive, versus, Site B: 35 negative to 33 positive). Clinicians at Site A frequently cited that MBC was artificial and was overly evaluative of the clinician's abilities. At Site B, clinicians endorsed concerns about how MBC would impact clinical productivity, the feasibility of MBC implementation, and the utility of MBC in achieving therapy goals. Simultaneously, clinicians at Site B indicated that MBC would be useful for evaluation and diagnosis and could be used to identify lack of progress. Clinic director participants indicated that leveraging technology for client completion would be essential.

**Implementation.** We then piloted a standardized implementation protocol consisting of (a) embedding the PHQ-9 into the electronic health record (requiring the clinician to verbally assess clients as tablets were not available), (b) a site-specific guideline for PHQ-9 use, and (c) a brief training. The 4-hour training content was based on the work of Persons, Hong, and Koerner (2012); topics included: MBC as a foundational framework; MBC clinical utility; the research evidence for MBC and the PHQ-9; the MBC protocol; research and IT supports to enact the protocol; introduction to the electronic health record interface; and steps for working with lack of progress. These strategies reflect a minimum set of discrete evidence-based implementation strategies that could be blended to facilitate implementation. Pre-training Intention to Use MBC scores were highly correlated with the frequency of subsequent PHQ-9 administration ( $r=.67$ ,  $p=.036$ ). Across sites, 67% MBC penetration was achieved (number of clinicians implementing MBC/number of participating clinicians). Site A achieved 44% penetration while Site B achieved 80% penetration. One limiting factor at Site A was technology problems as the new electronic health record had not yet been introduced and the PHQ-9 did not consistently show up for clinicians. Despite these relatively high penetration scores at the clinician level, this minimal standardized implementation protocol and site-specified MBC guideline resulted in 13.4% (Site A) and 38.6% (Site B) use of the PHQ-9 (by dividing number of administrations by total possible number of administrations) over the course of one year follow up. Unfortunately, we were unable to assess the differential effect of MBC implementation on client outcomes to determine whether adapted guidelines limited MBC's utility. These findings support the proposal in three ways: (a) they emphasize the utility of a

mixed methods needs assessment in identifying site differences in barriers, (b) they highlight the importance of tailoring strategies to barriers as this minimal standardized protocol led to superior outcomes in Site B where fewer barriers were present, and, (c) they underscore the potential importance of incorporating technologically advanced solutions for client PHQ-9 completion.

## **C10. Multifaceted Standardized and Tailored Implementation Conditions**

***Overview of the Blended Implementation Protocol.*** Both conditions (standardized and tailored) will employ the same blended protocol of implementation strategies to remove time and resource confounds (see Table 3). The guiding model (*Framework for Dissemination*; Figure 1; [name] et al., 2008), the best available literature on related efforts to promote MBC implementation (e.g., Evans & Hser, 2004; Harding et al., 2011; Lambert et al., 2005; Morris & Trivedi, 2011; Persons, Hong, & Koerner, 2012; Teruya, [name], Hser, & Evans, 2006), personal communication regarding program evaluation of a loosely tailored MBC implementation effort at Group Health clinics ([name], February 11, 2014), the MBC intervention framework, the partnership goals, and the pilot study defined the blended protocol of implementation strategies (Powell, McMillen, Proctor, et al., 2012). It was determined that embedding the PHQ-9 into the electronic health record was not sufficient but that using tablet computers would be essential to promote feasibility of implementation. The proposed local needs assessment is necessary to assess site-specific contextual factors and to identify opinion leaders and champions. In our pilot, we did not involve clinicians on the implementation team, but literature suggests this may be critical to achieving sustainment (Teruya, [name], Hser, & Evans, 2006) and it is consistent with our partnership goals. As such, each site will form an implementation team consisting of the PI, Co-I ([name]), the site administrator, a clinician identified as an opinion leader (via self-report; Childers, 1986), and a self-nominated MBC champion who will meet for at least 30 minutes prior to each triweekly consultation session. Training and consultation with experts are essential strategies for promoting clinician behavior change and fidelity to the intervention, particularly in the case of evidence-based psychosocial interventions (Herschell et al., 2010). A guideline will be set to specify the frequency of expected PHQ-9 administration with depressed clients. The order of strategies will proceed as follows within each site's 5-month active implementation period: (a) embed PHQ-9 in electronic health record; (b) conduct needs assessment; (c) form implementation team; (d) set guideline; (e) offer initial training; (d) conduct tri-weekly group consultation meetings (see C11. Overview of Study Design). In the 10 months post active imple-

mentation, the implementation team will be encouraged to continue to meet and

**Table 3. Standardized versus Tailored Protocol and Focus**

Contextual Factor	Strategies	Standardized Focus	Tailored Focus
Resources	PHQ-9 in EHR w/ Tablets	Client Completion on Tablets	Client Completion on Tablets
Networks & Linkages	Form Implementation Team	Monitor MBC Fidelity	To Identify Barriers
Policies and Incentives	Guideline	Each Session w/ Client	Determined by Site
Norms & Attitudes	Training	Standardized Protocol	Targets Barriers
Structure & Process	Progress Note Modifications	For Clinician Score Review	For Clinician Score Review
Media & Change Agents	Consultation with Experts	MBC Fidelity	Targets Barriers

consult with clinicians to promote sustainment. Table 3 depicts the protocol and unique focus of the implementation strategies across conditions. A similar blended protocol of implementation strategies led to successful MBC implementation using the PHQ-9 with 90% completion with over 30,000 clients each quarter at Group Health (personal communication, [name], February 11, 2014).

***Standardized Condition.*** The standardized condition includes all aforementioned strategies in the order listed above. The needs assessment will be conducted similar to our pilot study in that it is for data collection purposes only (i.e., no tailoring to identified barriers). The implementation team meetings will focus on monitoring MBC fidelity per the guideline. Depressed clients of clinicians in the standardized condition will be asked to complete the PHQ-9 prior to each session on a tablet in the waiting room

[figure not shown]
(guideline). PHQ-9 data will then be fed to the electronic health record for clinician review. Training will be offered to all enrolled clinicians using standardized material (described in [C9. Pilot Studies](#)). Consultation will focus on incorporating clinician review and discussion of PHQ-9 scores in session and providing tips on targeting lack of progress.

**Tailored Implementation Condition.** Tailored Implementation refers to the [responsive application of implementation strategies and content matched to determinants of practice \(i.e., barriers\) identified via a needs assessment](#). The same strategies outlined in the standardized condition will be employed in the tailored condition, but with content tailored to the site. The needs assessment will reveal contextual factors that may serve as barriers to the implementation process (focus groups will be analyzed using rapid ethnography methods; [C13b. Qualitative and Mixed Methods Data Analysis Plan](#)). An implementation team will convene to define the site-specific guidelines for PHQ-9 completion. For instance, it may be that Site X decides that monthly PHQ-9 administration is optimal with respect to feasibility and clinical utility. Conversely, Site Y may prefer to have clients complete the PHQ-9 every other session. Depressed clients of clinicians in the tailored condition will complete the PHQ-9 in the waiting room on a tablet computer prior to their appointment with the enrolled clinician based on the site-specific administration guideline. PHQ-9 data will then be fed to the electronic health record for clinician review. Training will be offered to all enrolled clinicians using tailored materials that will target the identified barriers from the needs assessment. For instance, if clinicians at a particular site perceive the PHQ-9 to be irrelevant to clients, training content will incorporate client perspectives on its utility. If clinicians indicate that lack of time is a barrier, then training will incorporate experimentation to streamline review and discussion of scores. The implementation team will focus on identifying remaining barriers for discussion in the triweekly group consultation session. Similar to the standardized condition, consultation will also focus on incorporating clinician review and discussion of PHQ-9 scores in session and providing tips on targeting lack of progress.

## **C11. Overview of Study Design, Timeline, Sample, and Data Collection**

The two years of planning and pilot studies in partnership with Centerstone have informed the implementation protocols as well as its overall research design and data collection procedures. We propose an effectiveness-implementation hybrid design type 2 to allow for simultaneous investigation of clinician- and client-level outcomes. This design will be a dynamic waitlist randomized pragmatic trial comparing the effect of a standardized versus a tailored approach to MBC implementation (Figure 2 & Table 4).

**Figure 2. Design Overview**

**Phase 1: Start-up/Pre-Implementation.** Months 0-8 will be characterized by preparatory work for the randomized trial. Little needs to be done to create the research infrastructure in the participating clinics given the existing role of Centerstone Research Institute directed by the proposal Co-I ([name]). We will prepare the tablet computers for client data collection. We will work with Netsmart ([name] [Letter of Support](#)) to link the electronic health record to the PHQ-9 and create the optimal interface for clinicians within the progress note. We will enroll the identified sites ( $N=12$ ), match sites based on size and urban/rural status, and randomize to either [early or later](#) stage implementation and to condition (standardized or tailored) (Brown et al., 2006). There will be four cohorts each with 5 months of active implementation and 10 months of sustainment monitoring. We will modify the progress note for clinicians to document fidelity (PHQ-9 discussed in session) and reasons for deviation ([C6. MBC Fidelity](#)). We will pilot the progress note modifications with our advisory board of clinic directors to maximize the information gleaned and to minimize the burden. Because of our use of technology, we will create IT

Frequently Asked Questions and instructions, which will be embedded within Centerstone's internal news. We will also interface study research assistants with clinic staff by attending regular staff meetings at each site. Finally, we will refine measures using established protocols (e.g., Norms; Francis et al., 2004).

**Phase 2: Randomized Trial: Implementation & Sustainment.** Implementation will take place across 12 sites in months 8-38 using the dynamic waitlist control design (Brown et al., 2006; C15. Justification and Feasibility). Specifically, matched sites (based on size and urban/rural status) will be randomized to either early or later stage implementation in 4 cohorts (2-4 sites per cohort spaced 5 months apart), with half the sites randomized to the standardized and half to the tailored condition; see Figure 2 for a concise depiction of the implementation timing. The timing of this protocol is based on the published work of Miller et al. (2012) as well as the successful naturalistic MBC implementation at Group Health (personal communication, [name], February 11, 2014). Beginning at month 8, the earliest cohort (2 sites) will engage in the baseline mixed methods needs assessment (Assessment Time 1; AT1). Using purposeful sampling (Palinkas et al., 2013), a subset of clinicians (N=5-8 at each site) representing extreme variation (nominated by clinic directors based on their support for or against MBC implementation) will participate in a 1.5-hour focus group. This sampling approach is critical to gain a wide range of clinician views. Rapid ethnography will then be used to uncover site-specific insights that will guide the content of training and consultation in the tailored condition only (with the aid of mixed method expert [name]; C13b. Data Analysis Plan). During the needs assessment, all enrolled clinicians will complete the battery of baseline measures (see Table 5, Section II), from which the opinion leader (Childers, 1998) and self-nominated MBC champion will be identified and invited to join the implementation team. Across conditions, this team will convene triweekly during the 5-month active implementation period to ensure implementation strategy fidelity (Proctor et al., 2013) and review MBC fidelity. Following the needs assessment, clinicians will participate in a 4-hour MBC training workshop (see C9. Pilot Studies for content) and will begin triweekly consultation. To characterize the differences in implementation team meetings and consultation between conditions, sessions will be audiorecorded and contextual factors logged by graduate research specialist on the MBC Barriers Log (informed by the Framework for Dissemination; [name] et al., 2008; see Appendix for form template). Simultaneously a site team member will log meetings (using the same form) and data triangulated to calibrate site team members and prep for the exit of research personnel. Implementation/Process Evaluations ([name] et al., 2008; AT2) at the clinician level will occur 5 months after the needs assessment at which point the research personnel will be removed. The site implementation teams will be encouraged to continue meeting to promote MBC sustainment and the responsibility to log and address MBC barriers will transfer completely to the site team members. Outcome/Impact Evaluation ([name] et al., 2008; AT3) at the clinician and client level will occur 10 months after the Implementation/Process Evaluation. Focus groups will be held with the implementation team at AT3 to review their experience and the site's progress since the research personnel exited the team. All aforementioned steps will be repeated across the remaining three cohorts.

**Phase 3: Post Hoc Characterization of MBC Fidelity, Data Analysis, and Manuscript Preparation.** Consistent with the Dynamic Sustainability Framework (Chambers, Glasgow, & Stange, 2013), the approach to MBC implementation has the potential to be adapted by sites in the tailored condition. That is, early in the active implementation process (within the first month), the implementation team will generate a guideline for MBC implementation that is specific to their site. Characterizing fidelity for this condition will need to reflect the guideline established for

ACTIVITIES	Table 4. Study Activities			
	YEAR 1	YEAR 2	YEAR 3	YEAR 4
Study Phase	Phase 1	Phase 2		Phase 3
EHR Modifications				
Clinician Enrollment				
Randomization				
Clinician Assessment				
Active Implementation	Co1	Co2	Co3	Co4
Sustainment Monitoring		10-months for each cohort		
Client Enrollment & Assessment				
Rapid Ethnography				
Qualitative Coding				
Data Analyses				
Characterize MBC Fidelity				
Manuscript Preparation				

Note. Co = Cohort (2-4 sites with 1-2 randomized to each condition).

each site. For instance, if a site set a guideline to administer the PHQ-9 monthly for each client then actual administration will need to be confirmed monthly. Data capture from the electronic health record will also include whether or not the clinician reviewed the PHQ-9 scores prior to or in session. Finally, with respect to coding of MBC review in session the clinician self-report (via the electronic health record) and client report (via automated phone survey) will be triangulated. Concurrently, focus group data will be formally coded (see *C13b. Qualitative and Mixed Methods Data Analysis*) for manuscript preparation.

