
### **C13b. Qualitative and Mixed Method Data Analysis Plan**

**Overview.** Mixed methods will be used to integrate findings from Aim 2 using a quantitative + qualitative structure (wherein both types of data are collected simultaneously) to achieve the function of data expansion for the purposes of evaluation and elaboration (Palinkas et al., 2011). We will use a connecting process (whereby the datasets build upon one another) and work closely with our mixed methods expert ([name]). Rapid ethnography (Millen, 2000) will be used to synthesize the needs assessment data only in the tailored condition to characterize participant experiences. Focus groups will be analyzed separately to characterize participant responses within each site, across conditions. Graduate student researcher ([name]), who was trained in qualitative inquiry methods during the pilot studies, will work with the postdoctoral fellow to train research assistants to identify and code analyzable units of meaning in the focus group transcripts. An iterative approach to coding will resolve disagreements through research team discussion. Inductive analyses based on emergent themes rooted in grounded theory will be conducted (using QSR N-Vivo software). Codes will also be assigned based on contextual factors using [name] et al.'s (2008) Framework of Dissemination. The final list of consensus codes will include themes established *a priori* and through emergent themes analysis.

Using the U.S. NIH guidelines for mixed methods best practices (Creswell, et al., 2011), we will connect the quantitative and qualitative datasets in QSR N-Vivo to allow for case-specific pattern identification and hypothesis testing. For example, we will enter clinician-specific MBC fidelity data

(categorized as “none”, “low”, “moderate”, “high”) and query each qualitative theme for matched clinician focus group quotes in order to investigate the influence of contextual factors on level of MBC fidelity. Based on pilot study qualitative findings, we anticipate that focus groups will yield both positive and negative valenced statements for each of the a priori and emergent themes. We will investigate the extent to which differences exist in the valence of contextual themes between conditions. This approach will allow us to distinguish factors that might explain the differences in the quantitative findings, and notably MBC fidelity.

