#### **Phase 2 (Months 8 – 38)**

*5-Month Active Implementation.* Beginning at month eight, clinicians who provide individual psychotherapy to adults with depression (based on their self-reported typical and current caseload (i.e., clinicians will learn in the eligibility discussion that if they consent to participate in the study then they must have eligible clients to potentially enroll as well) and who conduct psychotherapy sessions in English will engage in the baseline mixed methods needs assessment. This assessment will consist of a battery of surveys and then, following the completion of these surveys a focus group will take place. Clinicians will be asked to complete the following baseline battery of self-reports (Appendix A): Demographic Questionnaire ([name] & Simons, 2011; Appendix A.1); Progress Monitoring Theory of Planned Behavior (Francis et al., 2004; Appendix A.2); Attitudes toward Standardized Assessment-Monitoring and Feedback (Jensen-Doss et al., *in press*; Appendix A.3); Monitoring and Feedback Attitudes Scale (Jensen-Doss et al., *in press*; Appendix A.4); Monitoring As Usual Measure (Lyon et al., 2015; A.5); Evidenced-Based Practices Attitudes Scale (Aarons, 2004; A.6); Survey of Organizational Functioning (Broome et al., 2007; A.7), Implementation Climate (Jacobs et al., 2014; A.8); Implementation Climate Scale (Earhart et al., 2014; A.9); Barriers and Facilitators to Implementing Survey (Salyers, Rollins, McGuire, & Gearhart, 2008; A.10); Sociometric Questionnaire (Valente et al., 2007; A.11); Opinion Leadership Scale (Childers, 1986) and self-nomination question (A.12); Implementation Leadership Scale (Aarons et al., 2014; A.13); and Perceptions of Adopting Measurement-Based Care (Moore & Benbasat, 1991; A.14). All questionnaires will be completed online using assessment software by emailing them a link or via hard copy (in-person). These questionnaires will take about 60 minutes to complete and clinicians who complete the baseline assessment will receive \$50 compensation. Using the data from these surveys, a subsample of clinicians at each site, selected using purposeful sampling for extreme variation (Palinkas et al., 2013), will be asked to participate in a 1.5 hour focus group (Appendix E.1). Clinicians who participate in the focus group(s) will receive \$25 compensation. Focus groups will be recorded and transcribed with data de-identified for the purposes of qualitative coding. Staff who do not provide individual psychotherapy to adults with depression in English (for example, this could be clinicians who primarily provide therapy to children, groups, diagnoses other than depression and/or conduct therapy in another language; or psychiatrists, nurses, nurse practitioners, case managers, other non-clinical staff) will engage in an abbreviated version of the battery of self-report measures which will include: (Appendix A): Demographic Questionnaire ([name] & Simons, 2011; Appendix A.1); Progress Monitoring Theory of Planned Behavior (Francis et al., 2004; Appendix A.2); Attitudes toward Standardized Assessment-Monitoring and Feedback (Jensen-Doss et al., *in press*; Appendix A.3); Monitoring and Feedback Attitudes Scale (Jensen-Doss et al., *in press*; Appendix A.4); Evidenced-Based Practices Attitudes Scale (Aarons, 2004; A.6); Sociometric Questionnaire (Valente et al., 2007; A.11); Opinion Leadership Scale (Childers, 1986). All questionnaires will be completed online using assessment software by emailing them a link or via hard copy (in-person). The questionnaires will take less than 30 minutes to complete and staff who complete the abbreviated baseline assessment will receive \$20 in compensation per assessment point. Note, from this point forward we will refer to this group of staff as the “general staff” to differentiate them from those completing the full baseline battery which we will refer to as simply “clinicians.”

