Clinicians have the option of entering and reviewing the PHQ-9 data with clients in the EHR. When they enter the data they should be given the option of answering additional questions about if/why they reviewed scores with client (see Appendix B.2). Due to technological issues with the EHR, not all clinicians currently have the option of completing these questions. To ameliorate this issue, clinicians at affected sites will have the option of filling out this information on paper each week (see Appendix B.4-1, B.4-2). This data will then be collected in person by CRI staff who will transfer it to a secure database. To offset the inconvenience of filling out a paper version of the questions and to encourage clinicians to do so, \$1 will be included with each paper survey.

At the end of the 5-month active implementation, clinicians will be asked to complete the same questionnaires in the above-listed baseline battery. Similar to the baseline battery of self-reports, these assessments will be completed online or via hard copy, and clinicians will receive \$50 per assessment battery completed. In addition, a subsample of clinicians at each site similar to at the beginning of Phase 2 will be asked to participate in a 1.5 hour focus group (Appendix E.1). Clinicians who participate in the focus group(s) will receive \$25 compensation. A subsample of clinicians at each site will also be invited to participate in individual exit interviews regarding their views about and use of the PHQ-9 (Appendix A.21). Clinicians who participate will receive \$20 compensation.

*10-month Post-Implementation/Sustainment.* Towards the end of the post-implementation/sustainment phase, another focus group with a subsample of clinicians from each site selected via purposeful sampling will occur (Appendix E.1). Similar to the focus group at the beginning of Phase 2 and end of Phase 2, participants will be compensated \$25. The same aforementioned baseline and 5-month active implementation assessment battery will be re-administered towards the end of the 10-month post-implementation/sustainment phase to assess factors influencing sustainment of MBC. Similar to the assessments before, clinicians will receive \$50 for completing the assessment.

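### The plan gives two selection rules for the focus groups; under director nomination, the planned between-condition comparison of positive and negative views can partly reflect who was picked

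*Combined protocol and SAP*

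**What the plan says.** C11 (Phase 2: Randomized Trial) forms the baseline focus group at each site from 5 to 8 clinicians "representing extreme variation (nominated by clinic directors based on their support for or against MBC implementation". The reason it gives is breadth of opinion. Section VII (Clinicians, Phase 2) gives another route: "Using the data from these surveys, a subsample of clinicians at each site, selected using purposeful sampling for extreme variation". Directors are not mentioned there.

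Section V, part C, and C12a place site randomisation in Phase 1, before the focus groups begin at month 8. No section sets the number of supporters and opponents per site, conceals the condition from directors, or adjusts for stance at selection.

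C13b states the use of the material: "We will investigate the extent to which differences exist in the valence of contextual themes between conditions". It continues: "This approach will allow us to distinguish factors that might explain the differences in the quantitative findings, and notably MBC fidelity".

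For the 15-month assessment (AT3), C11 says "Focus groups will be held with the implementation team at AT3", while Section VII says that "another focus group with a subsample of clinicians from each site selected via purposeful sampling will occur".

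**The concern.** Choosing people for their stance is a sound way to hear the range of views. It is a weak basis for saying which condition holds the more positive views, because the share of positive statements depends on how many supporters and opponents were invited. That mix would be set after randomisation and at the directors' discretion, so randomisation does not balance it.

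At stake is the qualitative part of Aim 2. It could report that context was seen more favourably in one condition, and offer this as a reason for a fidelity difference, when some of the contrast came from group composition. The conflict matters in its own right too: with 12 sites in four staggered cohorts, staff working from different sections could select in different ways.

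**Working it through.** The plan states no sample size, error rate or effect size for this comparison, so there is no figure to reproduce. The check asks how large a difference selection alone could create when the two conditions hold identical attitudes.

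**Inputs from the documents**
- Group size: "a subset of clinicians (N=5-8 at each site" (C11).
- Allocation of the 12 sites: "with half the sites randomized to the standardized and half to the tailored condition" (C11), so 6 per condition.
- Pilot statement counts (C9): Site A, 44 negative and 17 positive; Site B, 35 negative and 33 positive.

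**Number of participants**
- Per condition: 6 × 5 = 30 to 6 × 8 = 48.
- In all: 60 to 96, or 60/150 = 40% to 96/150 = 64% of the target clinician sample.

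**Assumptions**
- Every clinician contributes equally many statements.
- Supporters' statements are positive with share s, and opponents' with share o. The documents give neither.
- Narrow gap: s = 49%, o = 28%. These are close to the pilot site averages, 33/68 = 48.5% and 17/61 = 27.9%, used only to set a scale.
- Wide gap: s = 70%, o = 20%.

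**Formula.** If the number of supporters per site differs by k out of n between the conditions, in the same direction across the sites of a condition, then

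spurious difference in positive share = (s − o) × k/n.

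| Gap | k | n = 5 | n = 8 |
|---|---|---|---|
| Narrow (0.21) | 1 | 4.2 points | 2.6 points |
| Narrow (0.21) | 2 | 8.4 points | 5.2 points |
| Wide (0.50) | 1 | 10.0 points | 6.2 points |
| Wide (0.50) | 2 | 20.0 points | 12.5 points |

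With k = 0 the difference is zero: the same mix in both conditions creates no bias.

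**Chance imbalance only.** Suppose each nominee is a supporter with probability one half, independently. The between-condition difference then has mean zero and standard deviation (s − o) × √2 × √(0.25/(6n)). This is 2.7 points (n = 5) or 2.1 points (n = 8) for the narrow gap, and 6.5 or 5.1 points for the wide gap.

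**The two AT3 statements.** C11's group consists of the implementation team, which looks back on its experience after the research staff left. Section VII's group is a clinician subsample. Both can be held. The plan does not say whether they are two groups, or which one enters the C13b comparison.

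**The case against.** The best defence is that one rule serves both conditions. Selection alone then gives an expected difference of zero unless the mix shifts systematically with condition, and nothing in the documents shows that it would. This stands, and it limits the point to a possible bias.

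It is also fair that extreme-variation sampling was chosen openly for breadth, that C13b describes elaboration and factors that might explain a result, and that the Specific Aims call Aim 2 exploratory. The Aim 2 mediation models in C13a use clinician surveys and the reasons for deviation recorded in the health record. Neither co-primary outcome uses the focus groups. All of this stands and confines the reach of the problem. It does not resolve which selection rule applies, nor does it fix the mix.

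Three stronger readings are tempting, and the documents do not support them:
- A reader might infer that directors at tailored sites would send more opponents, because the focus group shapes training there and is for data collection only at standardized sites (C10). No section speaks to directors' motives, and their knowledge of the condition is itself inferred from timing.
- A reader might infer that moving to the implementation team at AT3 would look like an improvement in attitudes. C13b plans no comparison over time. The opinion leader is found by a leadership scale, not by support for MBC, and Section VII adds a client and an office professional to the team.
- A reader might take the two AT3 descriptions as a contradiction. They are compatible if both groups are held.

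One could also object that choosing high and low scorers still selects on attitude. It does, but the mix is then the same by design in both conditions.

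**Conclusion.** The point holds in a limited form. C11 and Section VII give different selection rules and must be reconciled. If C11's nomination is followed, the planned comparison of views is open to selection after randomisation on the very feature being compared.

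It would go too far to say that the result simply shows who was picked, since that needs a mix that differs by condition. For a difference of one nominee per site in a consistent direction, the spurious gap is about 3 to 10 points, and for two nominees about 5 to 20. Both ranges rest on assumed shares of positive statements and equal contributions per clinician. Unsystematic imbalance would typically be about 2 to 6.5 points (one standard deviation) under the same assumptions. The consequence is confined to the qualitative part of Aim 2.

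**What to change.** 1. In C11, delete nomination by clinic directors and adopt Section VII's selection from the baseline survey. Research staff invite the same fixed number, or proportion, of high and low scorers at every site in both conditions. Name the attitude scale in advance, since Table 5 and the Section VII battery list different ones, and define high and low in advance.
2. In C13b, report positive and negative themes by condition within the high and low strata, as descriptive findings. Give the baseline scores of those who attended, by condition.
3. Take any overall attitude difference between conditions from the survey scores of all enrolled clinicians.
4. State whether the implementation-team group at AT3 is additional to the clinician subsample. If it is, analyse it separately.

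The cost is a change of wording. The surveys and focus groups are already planned, and Section VII already puts the survey first. The survey must be scored before invitations go out, and the make-up of each group becomes less flexible. The breadth of views that C11 wants is kept.
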